5.9. Interim Analyses

One planned, formal interim analysis on the primary efficacy endpoint will be performed by the DSMB-associated statistician after 50% of the anticipated participants has been adjudicated for hemostatic efficacy. DSMB will evaluate the results and recommend altering or stopping the study in the event of efficacy. Enrollment will not be paused during the interim analysis.

5.9.1. Stopping Criterion Due to Efficacy at Interim

The overall type I error for the interim and final analyses is controlled at 5% by employing the alpha spending function by Lan and DeMets based on Pocock boundaries (DeMets, 1994). If the interim p-value is < 0.0310 for comparing and exanet and UC in the primary endpoint analysis, DSMB may recommend stopping the study. In this case, the efficacy results from the interim analysis (with 50% of the anticipated participants) will be used for regulatory communication and submission. Enrollment of participants will proceed without interruption while the analysis is ongoing, resulting in > 50% of the anticipated participants in the final data cutoff; efficacy analysis on the final data cutoff will be considered as a sensitivity analysis.

5.9.2. Sample Size Re-estimation at Interim

If the DSMB recommendation at interim is to continue the study, a preplanned SSR will be performed by the DSMB-associated statistician with the interim data. The SSR will be based on a conditional power (CP) of comparing andexanet and UC at the final analysis (n=900), given the interim data, using a promising zone between 30% and 90% (Mehta, 2011). The assumption used for CP calculation is that the rate of hemostatic efficacy in andexanet and UC at the final analysis is 80% and 70%, respectively. Based on the observed CP, DSMB will recommend:

- No increase in the sample size, if the CP < 30% or > 90%
- An increase in the sample size to up to 1200, if $30\% \le CP \le 90\%$

5.9.3. Primary Analysis if Study is Continued from Interim

When no change in the sample size occurs (ie, interim decision to keep the original planned sample size), the conventional CMH statistics will be used at the final analysis to determine statistical significance (Wassmer, 2016).

In contrast, if the total sample size is increased per interim analysis decision, then the final analysis will use the weighted statistic proposed by Cui, Hung, and Wang (1999).

In this case, the test statistic at the final analysis is a weighted sum of the test statistic at the interim analysis (Stage 1: n1 = 450), and the test statistics based on additional participants (Stage 2: n2 = 750); the weight is 0.5 to avoid introducing bias. The weighted statistics is calculated as follows:

$$Z_{\rm CHW} = \sqrt{w} \, Z_1 + \sqrt{1 - w} \, Z_2$$

where w = 0.5, Z_1 and Z_2 are the CMH test statistics at Stage 1 and Stage 2, respectively.

5.10. **DSMB and Other Committees**

Each of the planned study committees will have a charter outlining its activities and responsibilities. Interim monitoring of efficacy and safety data will be performed periodically by the DSMB as described in the DSMB charter. The DSMB may also recommend termination of the study for any safety concern that is felt to outweigh potential benefits.

In brief, the purpose of each committee is as follows:

- Independent EAC: The EAC will oversee the adjudication of effective hemostasis within the first 12 hours post-randomization. In addition, all TEs and deaths will be adjudicated. The EAC will remain blinded to treatment assignment for all participants. Details for the EAC are located in the EAC Adjudication Charter.
- Independent DSMB: The DSMB will monitor all safety and efficacy data, evaluate the interim analysis performed by the unblinded independent DSMB statistician, and make recommendations for study modification or stopping due to efficacy or safety reasons. Details for the DSMB are located in the DSMB Charter.

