- Andexanet will be given via an IV bolus administered over approximately 15 minutes (low dose) to 30 minutes (high dose), followed immediately by a continuous infusion administered over approximately 120 minutes. There will be no crossover between treatment groups.
- The study duration for most participants will be up to 37 days. The study duration includes 3 study periods as follows:
 - Screening and Baseline Periods: < 1 day (Day 1)
 - Treatment Period: < 1 day (Day 1)
 - Follow-up Period (all adverse events [AEs], survival, and antibodies): 30 days (Day 1 to 30 study visit)

Participants with a positive anti-andexanet antibody response at the Day 30 visit will have an additional visit approximately 120 days post-randomization or within 30 days from when the positive test is made known to the Investigator, whichever is later.

- The primary efficacy endpoint is effective hemostasis (excellent or good versus poor/none versus nonevaluable), based on assessment of neurologic status determined by National Institutes of Health Stroke Scale (NIHSS), the use of rescue therapy, and hematoma expansion evaluation at 12 hours post-randomization by an imaging scan (computed tomography [CT] or magnetic resonance imaging [MRI]). Effective hemostasis will be determined by an adjudication algorithm or will be adjudicated by a blinded Endpoint Adjudication Committee (EAC). The derivation of effective hemostasis is provided in Section 6.1. Refer to separate Adjudication Charter for further information.
- The EAC will also adjudicate all thrombotic events (TEs), which are reported as AEs and all deaths. TEs are adverse events of special interest (AESIs) for the study.
- Approximately 900 participants are planned to be enrolled in the study at approximately 250 sites in North America, Europe, and Asia.
- A formal interim analysis for efficacy will be performed when approximately 50% (450 participants) of the anticipated sample size has been adjudicated. The main purposes of the interim analysis are 1) to assess whether to stop the study early due to efficacy and 2) to evaluate safety. Interim analysis will be performed by an independent statistics group and evaluated by the Data Safety Monitoring Board (DSMB). Details regarding the interim analysis are presented in Section 5.9.

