2. STATISTICAL HYPOTHESES

The primary objective of this study is to compare the rate of effective hemostasis between and exanet and UC group. The following hypothesis will be evaluated:

Ho:
$$\pi_{UC} - \pi_{andexanet} = 0$$

HA: $\pi_{UC} - \pi_{andexanet} \neq 0$

where π is the rate of effective hemostasis in each group.

Comparison will be performed using a Cochran-Mantel-Haenszel (CMH) test stratified by time from symptom onset to the baseline imaging scan (< 180 minutes versus \geq 180 minutes). The difference in the proportion of participants with effective hemostasis between andexanet and UC group, the corresponding 95% confidence intervals (CIs) for the difference, and the p-value for the comparison will be provided.

The analysis of efficacy will employ an alpha spending function by Lan and DeMets based on Pocock boundaries. The primary efficacy objective of the study will be considered met if the proportion of participants with effective hemostasis in the andexanet group is statistically significantly higher than that in the UC group at interim (p < 0.0310) or in the final (p < 0.0277) analysis.

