3. SAMPLE SIZE DETERMINATION

Results (as of 30 Jun 2020) from the Phase 3b/4, single-arm, open-label Study ANNEXA-4 have shown that the rate of effective hemostasis is 79% (95% CI: 74% to 84%) based on evaluable participants with ICrH; the rate of effective hemostasis is 80% (95% CI of 75% to 84%) based on 340 efficacy-evaluable participants with all types of bleeding.

Based on these results, it is assumed that the rate of effective hemostasis in this study is 70% and 80% for participants treated with UC and andexanet, respectively. The 10% absolute difference represents a 33% risk reduction of not achieving effective hemostasis by andexanet as compared to UC, which is considered clinically meaningful. After accounting for early discontinuation rate and one interim analysis, it is estimated that a total sample size of approximately 900 participants (ie, 450 participants per group) will have approximately 90% power to detect a 10% absolute difference between andexanet and usual care in the rate of effective hemostasis at a 0.05 two-sided overall significance level.

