5.3. Primary Endpoint Analysis

The primary objective of the study is to compare the rate of participants with effective hemostasis 12 hours post-randomization between and exanet and UC. The primary endpoint is based on the achievement of effective hemostasis, as determined by the blinded EAC based on prespecified criteria documented in the Adjudication Charter.

Effective hemostasis will be further defined as follows:

- 1 = for participants with effective hemostasis rated as excellent/good
- 0 = for participants with effective hemostasis rated as poor/none

Refer to Section 6.1, for details on how the primary efficacy endpoint is determined, including the handling of missing data.

The primary analysis will be performed on the ITT Set.

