5.3.1. Estimand

Table 3 below describes the attributes of the Primary (Composite) estimand.

Page 17 of 52 Alexion Confidential

Estimand	Attributes of Estimand				
	Treatment	Endpoint	Population	Intercurrent Events Handling	Statistical Summary
Primary (composite estimand)	Andexanet vs usual care	Proportion of participants with effective hemostasis	ITT Set	Rescue medications/procedures: All participants will be considered as poor/none (not effective) for effective hemostasis if meeting Criteria 1 and/or 2 below: 1. Initiation of rescue therapies (medication or procedures) starting ≥ 3 hours post- randomization and up to < 12 hours post-	Difference in the proportion of participants with effective hemostasis between the 2 treatment groups, and its 95% confidence interval as estimated by a CMH test stratified by the time from symptom onset to baseline imaging assessment (< 180 minutes vs ≥ 180 minutes)

Table 3:Attributes of Primary (Composite) Estimand

Estimand	Attributes o	of Estimand			
	Treatment	Endpoint	Population	Intercurrent Events Handling	Statistical Summary
				change from baseline to 12 hours in hematoma volume.	
				 Core imaging laboratory request for EAC review. 	
				4. Misadministration of procoagulant blood products contrary to treatment allocation within 3 hours pos-randomization (including andexanet in usual care arm)	
				5. Performance of a surgery or interventional procedure to treat the index hematoma or that could impact hematoma volume within 3 hours post- randomization	
				Nonevaluable events : There are 2 types of reasons for nonevaluable hemostatic status:	
				 Cases deemed nonevaluable due to administrative reasons (for example, but not limited to, follow-up scan not available, not performed not 	
				performed, not interpretable, or transfer of the participant to another facility for administrative purposes)	
				 Cases deemed nonevaluable due to clinical reasons (for example, but not 	

Table 3:Attributes of Primary (Composite) Estimand

Estimand	Attributes of Estimand					
	Treatment	Endpoint	Population	Intercurrent Events Handling	Statistical Summary	
				limited to, the participant died due to index bleed or the participant had unplanned surgery draining hematoma) The decision of the EAC is considered final. The nonevaluable status due to both reasons will be treated as poor/none in the primary analysis.		

 Table 3:
 Attributes of Primary (Composite) Estimand

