5.3.2. Main Analytical Approach

Primary analysis will be performed using a CMH test stratified by time from symptom onset to the baseline imaging scan (< 180 minutes versus \geq 180 minutes). The difference in the proportion of participants with effective hemostasis, its 95% CI, and the p-value will be estimated.

A by-participant listing of effective hemostasis will be provided.

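### At the final analysis the reported 95% CI does not match the test (p < 0.0277, and CHW-weighted after a sample-size increase), so it can lie above zero when the trial has failed

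*SAP*

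**What the plan says.** **Level of the test.** SAP section 2 declares the primary objective met if andexanet is significantly better "at interim (p < 0.0310) or in the final (p < 0.0277) analysis". SAP 5.1.1 and Protocol 10.5.4.2 give the same two levels. They come from "employing the alpha spending function by Lan and DeMets based on Pocock boundaries" (SAP 5.9.1), with the interim "when approximately 50% (450 participants) of the anticipated sample size has been adjudicated" (SAP 1.2).

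**Interval.** SAP 5.3.2 states: "The difference in the proportion of participants with effective hemostasis, its 95% CI, and the p-value will be estimated". Table 3 in SAP 5.3.1 names, as the estimand's statistical summary, the difference and "its 95% confidence interval as estimated by a CMH test stratified by the time from symptom onset to baseline imaging assessment". On the analysis set, SAP 5.3 says: "The primary analysis will be performed on the ITT Set". The level is 95% wherever an interval for the primary endpoint is mentioned, in both documents.

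**Final test.** Under SAP 5.9.3 and Protocol 10.7.3 the conventional CMH statistic is used if the sample size is unchanged. However, "if the total sample size is increased per interim analysis decision, then the final analysis will use the weighted statistic", with stage sizes 450 and 750 and w = 0.5. Neither section says what estimate or interval accompanies the weighted statistic. Neither document contains an alpha-adjusted, repeated or CHW-weighted interval.

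**The concern.** Test and interval differ in two ways at the final analysis.

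- **Critical value.** The test uses 2.201 and the interval 1.960.
- **Stage weights, only after an increase.** The test gives stage 1 a weight of 0.5. An ordinary analysis of all 1200 participants gives it 450/1200 = 0.375.

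The interval is the more permissive of the two. A trial could fail its error-controlled test and still report, as the summary its estimand table names, a 95% CI wholly above zero. This would tend to occur at moderate effects, which is where the sample-size re-estimation is meant to operate, and it would invite a positive reading of a failed trial.

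**Working it through.** **1. The plan's own levels.** Pocock-type spending at information fraction 0.5 is 0.05 × ln(1 + (e − 1) × 0.5) = 0.0310. Solving for the final bound with correlation √0.5 between looks gives c = 2.201, p = 0.0277. Both figures reproduce. The matching confidence levels are 1 − 0.0310 = 96.90% and 1 − 0.0277 = 97.23%.

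**2. No increase, N = 900.** These examples use an unstratified pooled-variance Z in place of the CMH statistic, and a Wald interval. With usual care at 315/450 (70.0%):

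| Andexanet | Difference (points) | p | 95% CI (points) | 97.23% CI (points) | Test |
|---|---|---|---|---|---|
| 343/450 | 6.2 | 0.035 | 0.4 to 12.0 | −0.3 to 12.7 | fails |
| 344/450 | 6.4 | 0.029 | 0.7 to 12.2 | −0.04 to 12.9 | fails |
| 345/450 | 6.7 | 0.024 | 0.9 to 12.4 | 0.2 to 13.1 | met |

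Observed differences from about 5.8 to 6.5 points give a 95% CI above zero and a failed test. The 97.23% interval agrees with the test in each row.

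**3. Increase to N = 1200.** The stage-wise drift at 80% against 70% is 0.10/√(0.37/225) = 2.466, so CP = Φ(Z1 + 2.466 − 2.2015√2). The 30-90% zone is then Z1 from about 0.12 to 1.93.

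Example: andexanet 166/225 then 287/375; usual care 158/225 then 262/375.

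- Stage 1: d1 = 8/225 = 0.0356, SE1 = 0.0423, Z1 = 0.840, CP = 58%.
- Stage 2: d2 = 25/375 = 0.0667, SE2 = 0.0323, Z2 = 2.061.
- CHW: √0.5 × (0.840 + 2.061) = 2.051, p = 0.040. The test fails.
- Ordinary analysis of all 1200: difference 5.5 points, 95% CI 0.5 to 10.5.
- CHW inversion: √0.5/SE1 + √0.5/SE2 = 38.56; estimate 2.051/38.56 = 5.3 points; half-width 2.2015/38.56 = 5.7 points; interval −0.4 to 11.0. This agrees with the test.

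With 285/375 in stage 2 the CHW p-value is 0.0535, yet the ordinary 95% CI is 0.1 to 10.2. With 288/375 even the ordinary 97.23% lower limit is +0.02 points while CHW p = 0.0347. Correcting the level alone is therefore not enough after an increase.

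**4. How often.** Simulation of the plan's rules, 3 million trials per effect: interim stop beyond 2.157, increase to 1200 when Z1 is in the zone, final bound 2.201. Entries are the chance that the interval lies above zero while the final test fails.

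| True effect (points) | 0 | 3 | 5 | 7 | 10 |
|---|---|---|---|---|---|
| 95% CI, all trials | 1.1% | 6.3% | 9.4% | 7.7% | 1.8% |
| 95% CI, trials with an increase | 2.2% | 9.1% | 13.4% | 12.5% | 4.9% |
| Ordinary 97.23% CI, trials with an increase | 0.3% | 1.7% | 2.8% | 3.0% | 1.4% |

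The opposite conflict, a test met with a 95% CI that includes zero, did not occur in the simulations.

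**5. Width.** Without an increase the ratio is 2.2015/1.960 = 1.12. With one, it is [2.2015/(√0.5 × (√450 + √750))]/[1.960/√1200] = 0.0641/0.0566 = 1.13.

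**The case against.** **No decision uses the interval.** Success is judged on the p-value alone, CHW at 0.0277 is a pre-specified test, and SAP 5.3.2 reports the p-value beside the interval. This stands. A reader might infer that the mismatch inflates the type I error or changes the trial's conclusion; the documents do not support that.

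**A 95% CI beside an alpha-adjusted p-value is common, and the weighting is the smaller cause.** Both parts are true. Once the level is corrected, only 0.3-3% of trials with an increase still conflict. But Table 3 makes this interval the estimand's summary, so it should not be able to point the other way from the test with nothing said about it.

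**The SAP never says that the stages are pooled for the interval.** Correct. That is an inference from the only interval defined, the CMH interval on the whole ITT Set. Strictly, the interval after an increase is left unspecified.

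**A reader might also infer that the 95% CI under-covers at the final analysis.** That does not hold as a general statement. Over the whole procedure, coverage at true effects of 0-5 points does fall to about 94%. The shortfall comes from trials stopped at the interim, where coverage is 0%, 66% and 86% at 0, 3 and 5 points. At those effects coverage is about 96% among continuing trials and 96-98% after an increase. At 10 points, coverage among continuing trials is 93.7%, but overall it is 95.1%. Under-coverage is not part of this point.

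**Conclusion.** The point holds as a reporting defect. Followed as written, the SAP can present a 95% CI above zero for a trial that failed its primary test. This occurs in about 1%, 6%, 9%, 8% and 2% of all trials at true effects of 0, 3, 5, 7 and 10 points. At the planned 10-point effect it is uncommon, because most such trials stop at the interim. The level mismatch is the main cause; the missing CHW-matched estimate and interval add a smaller part after an increase.

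The rates assume usual care near 70%, an unstratified approximation to CMH, no dropout, a stop whenever the interim bound is crossed (the SAP says the DSMB may recommend it), and increases always to 1200 (the SAP allows up to 1200). The level mismatch itself depends on none of these.

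**What to change.** In SAP 5.3.2, report beside the primary test an interval at the level of that test: 97.23% at the final analysis and, by the same logic, 96.90% at the interim.

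In SAP 5.9.3, state that after an increase the estimate and interval come from inverting the CHW statistic, with stage-wise stratified differences d1, d2 and standard errors SE1, SE2:

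- estimate = (√w·d1/SE1 + √(1−w)·d2/SE2) / (√w/SE1 + √(1−w)/SE2)
- half-width = 2.201 / (√w/SE1 + √(1−w)/SE2)

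Define the SEs consistently with the CMH statistics. Those use a null variance, so plain Wald SEs could leave small conflicts at the boundary. Keep the conventional 95% CI, labelled as descriptive.

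The cost is a few sentences of SAP text, with no change to design, alpha, power or data. The downside is a decision interval about 12-13% wider than the conventional one.

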5.11. Handling of Laboratory Samples Out of Stability

If there are bioanalytical samples for assessing anti-fXa activity out of stability window due to reasons such as change in the bioanalysis provider, an additional analysis excluding samples out of stability windows may be performed to evaluate the impact of stability issue. This applies to the following analyses:

Secondary analysis for percent change from baseline to nadir in anti-fXa activity by ranked ANCOVA (Section 5.4)

Correlation analysis between effective hemostasis and percent change from baseline to nadir in anti-fXa activity 2 hours post-randomization (Section 5.5.7)

6. **SUPPORTING DOCUMENTATION**

6.1. Appendix 1: Technical Specifications for Derived Variables

The following derived data will be calculated prior to the analysis:

Defining the Per Protocol Set

The Per-Protocol Set (PPS) will include all participants in the ITT Set who did not have important protocol deviations impacting the primary hemostatic efficacy endpoint.

The reasons for exclusions and inclusion from the PPS will include the following subset of major protocol deviations:

- Inclusion/Exclusion:
 - Participant failed the following inclusion/exclusion:
 - Inclusion Criterion #3: An acute intracerebral bleeding episode of specified volume requirements
 - Even if the locally determined intracerebral bleed volume is out of per-protocol requirement, if subsequent average core lab screening volume assessment is within per-protocol requirements, then participant is eligible for PP set.
 - Inclusion Criterion #4: Performance of a head CT or MRI scan demonstrating the intracerebral bleeding within 2 hours prior to randomization
 - If CT/MRI scan is performed out-of-window/missing: If the EAC can determine an efficacy outcome, then participant is considered in PP set.
 - Inclusion Criterion #5: Specific treatment regimens and associated anti-fXa testing requirements with an FXa inhibitor
 - If central lab baseline/screening value collected within 2 hours of randomization or pre-treatment administration is >100ng/ml then participant is included into PP set
 - Inclusion Criterion #6: Where such timing is collected, time from bleeding symptom onset prior to the baseline imaging scan.
 - Inclusion Criterion #9: NIHSS score ≤ 35 at the time of consent (Protocol Amendment #2 only)
 - If NIHSS is performed out-of-window/missing: If the EAC can determine an efficacy outcome, then participant is considered in PP set.
 - Exclusion Criterion #1: Planned surgery affecting hematoma volume within 12 hours after randomization

- Exclusion Criterion #2: GCS score < 7 at the time of consent unless intubated and/or sedated for non-neurologic reasons <2 hours of consent
 - If GCS performed at informed consent is missing, then participant is excluded from PP set
 - Lack of evidence for intubation/sedation for non-neurological reason, then participant is excluded from PP set
 - If GCS is out-of-window; so long as the GCS documented is pre-treatment administration and >7, participant may be included into PP set.
- Exclusion Criterion #10 (PA #2) or #11 (PA #1, Original protocol): Receipt of restricted drugs or blood products within 7 days prior to consent
- Exclusion Criterion #11 (PA #2) or #12 (PA #1, Original protocol):
 Past use of andexanet (or planned use of commercial andexanet)
- Exclusion #13 (Original protocol, PA#1) or #12 (PA #2): Treatment of investigational drug <30 days prior to consent
- Exclusion Criterion #16: NIHSS Score >35 at time of consent (PA #1 only)
 - See appliable exceptions in section above 'Inclusion Criterion #9: NIHSS score ≤ 35 at the time of consent (Protocol Amendment #2 only)'
- Randomization:
 - The wrong study treatment is assigned post-randomization:
 - Use of pro-coagulant blood products or haemostatic agent for participant randomized to and exanet <3 hours post randomization where and exanet is not administered within 3 hours post randomization.
 - Use of and examet for participant randomized to usual care <12hrs post randomization
 - Study treatment is given prior to randomization
- Investigational Product (Andexanet) Administration:
 - Missing dose or Treatment administered incorrectly:
 - Wrong bolus dose
 - Low and examet bolus dose if < 360mg administered
 - High and exanet bolus dose if < 720mg administered
 - Wrong infusion dose
 - Low and exanet infusion dose if < 432mg administered

Page 35 of 52 Alexion Confidential

- High and exanet infusion dose if < 864mg administered
- Start of bolus is >30 minutes after randomization and either >2 hours of baseline imaging scan or >6 hours of symptom onset
- Start of infusion is >15 minutes after end of bolus
- There is a mismatch between recommended and examet dose regimen and actual dose administered such that:
 - Subject assigned high dose but receives low dose and examet is excluded from PP set
 - Subjects assigned low dose but receives high dose and exanet are eligible for PP set.
- Procedural:
 - 12hr NIHSS assessments performed by assessor unblinded to participant's treatment allocation
 - Unless the EAC is able to determine hemostatic efficacy for affected participants, the following will render the participant not evaluable for the Per Protocol Set if EAC concludes the participant is 'Nonevaluable due to administrative reasons'.
 - NIHSS:
 - Missing NIHSS score at baseline and/or 12 hours postrandomization
 - Baseline NIHSS score is >2 hours prior to randomization or post-randomization
 - 12 hour NIHSS score is <11 hours or >13 hours postrandomization
 - Confounded assessments (eg crossover or due to sedation or intubation)
 - Imaging (CT or MRI):
 - Imaging is missing at baseline and/or 12 hours post-randomization
 - Baseline imaging is >2 hours prior to randomization or postrandomization
 - 12-hour imaging is <11 hours or >15 hours post-randomization
 - Confounded assessments (eg inconsistent imaging modality)

Effective Hemostasis

Effective hemostasis is assessed based on image evaluation (CT or MRI), NIHSS score, and use of rescue therapy and categorized into excellent, good, or poor/none. Imaging will be performed at baseline and 12 hours post-randomization and should utilize a consistent imaging modality for both time points to minimize technical discrepancy (ie, CT or MRI scan). NIHSS evaluation

Page 36 of 52 Alexion Confidential (blinded or unblinded) to inform effective hemostasis will be performed at baseline (prior to randomization) and at 2, 3, 6, and 72 hours post-randomization. Blinded NIHSS evaluation will occur at 12 and 24 hours post-randomization. Use of rescue therapy (including procedures intended to treat the hematoma) between > 3 and < 12 hours post-randomization will be considered a treatment failure (ie, poor/none effective hemostasis).

Effective hemostasis will be further defined as follows:

- 1 = for participants with effective hemostasis rated as excellent/good
- 0 = for participants with effective hemostasis rated as poor/none

For a participant to have excellent or good effective hemostasis, he or she must meet all of the following criteria:

- An NIHSS score of less than +7-point change from the baseline score at 12 hours post-randomization
- An increase of no greater than 35% from baseline in hematoma volume between baseline and 12 hours post-randomization
- No rescue therapy received between 3- and 12-hours post-randomization

The majority of cases will not require review by adjudicators as the outcome rating will be obvious based on the core laboratory interpretation, NIHSS scores, and lack of additional treatments or procedures. An algorithm will be applied to the data from the imaging core laboratory and information provided by the sites on CRFs. The algorithm will determine if the case can be immediately classified as excellent, good, or poor/none or whether the case requires review by adjudicators and additional review by the EAC. Cases will be referred for EAC review, if the change in hematoma volume is < 35% and the change in the NIHSS score between baseline and 12 hours is < 7 and if one of the following criteria is met:

- baseline or 12-hour scans (11 to 15 hours post-randomization) missing, uninterpretable, or fall outside the collection window.
- NIHSS scores missing or fall outside the collection window for either baseline or 12-hour evaluations.
- Cases where the blinded imaging core laboratory readers indicate that review by the EAC is needed (or 3 readers disagree on classification of hematoma volume change).
- Cases where the participant was either sedated or intubated for either baseline or 12-hour NIHSS assessment (or both).
- Documented procedures that could potentially drain hematoma between 3- and 12hours post-randomization.
- Cases, where it is determined that there is insufficient information or where it is not otherwise possible to properly assess the effect of treatment, will be further classified by the EAC as follows:
 - Nonevaluable due to administrative reasons (eg, follow-up scans not available/performed/interpretable and the participant transferred to another

facility for administrative purposes); these participants will be analyzed as having poor/none effective hemostasis.

• Nonevaluable due to clinical reasons (eg, the participant died and the participant had unplanned surgery draining hematoma); these participants will be analyzed as having poor/none effective hemostasis.

Identifying Rescue Medications/Procedures

Rescue medications are identified from the concomitant medication CRF pages based on the following:

- 1. If indication for medication is "TO ACHIEVE HEMOSTASIS FOR CONTINUOUS (WORSENING) INTRACEREBRAL HEMORRHAGE BLEED," "TO ACHIEVE HEMOSTASIS FOR INITIAL BLEED," or "TO ACHIEVE HEMOSTASIS FOR NEW BLEED RE-BLEED" (except for tranexamic acid, which is permitted regardless of indication).
